SOP	Standard Operating Procedure

Study Summary

Title	Comprehensive Single-Cell Transcriptional Analysis of Aromatase Inhibitor-Resistant Breast Cancer
Running Title	Single cell sequencing for aromatase inhibitor-resistant breast cancer.
Phase	Pilot
Subject Participation Duration	2-8 weeks
Single or Multi-Site	Single site
Objectives	To comprehensively evaluate differences in tumor microenvironment subpopulations in AI-sensitive vs. AI-resistant HR+ breast cancer.
Number of Subjects	50 patients
Diagnosis and Main Inclusion Criteria	
1. Female \geq 18 years.2. Postmenopausal and suitable to receive aromatase inhibitor as per physician's discretion.3. Histologically confirmed un-resected operable invasive adenocarcinoma of the breast \geq 0.5 cm with estrogen receptor (ER) and/or progesterone receptor (PR) positive \geq 10%, and no human epidermal growth factor receptor 2 (HER2) amplification or overexpression.4. Patients must not have received any prior chemotherapy, radiation therapy, or endocrine therapy for their current breast cancer. Patients who received tamoxifen or raloxifene or another agent for prevention of breast cancer may be included.
Study Product, Dose, Route, Regimen	Letrozole 2.5 mg oral daily (standard of care)
Duration of Administration	2-8 weeks
Reference therapy	N/A
Statistical Methodology	This is a pilot study to evaluate the difference in tumor microenvironment subpopulation in AI-sensitive vs. AI-resistant HR+ breast cancer.

1 Introduction

This document is a protocol for a human research study. This study will be carried out in accordance with the applicable United States government regulations and Mayo Clinic research policies and procedures.

Aromatase inhibitor is currently the cornerstone standard of care endocrine therapy for patients with hormone receptor positive breast cancer. This is a pilot study to evaluate in-depth transcriptomic analysis using single cell sequencing technology to evaluate the effects of aromatase inhibitor not only in cancer breast cell but also noncancerous cells in the tumor microenvironment.

1.1 Background

In-depth transcriptomic analysis for each subpopulation in the tumor microenvironment of pre-treatment and post-treatment tumor samples obtained from AI-sensitive vs. AI-resistant patients will be performed using single-nucleus RNA-sequencing (snRNA-seq) (Figure 1). Re-clustering of stromal cells into sub-clusters will be undertaken to uncover hidden transcriptomic heterogeneity and to identify transcription factor regulation signatures that define these sub-clusters. Validation of transcriptome data will be performed using qPCR and immunofluorescence staining of cultured flow-sorted cells from human tissue sections and immunohistochemistry of these sections. We also seek to study the interactions between spatially distinct stromal sub-clusters and other cells (tumor, immune and endothelial) that will be studied by annotating our dataset with curated human ligand-receptor pairs. In turn, this will shed light on the role of stromal sub-clusters on modulating immune activation vs. tolerance/evasion via recruitment/exclusion and/or (dys)regulation (exhaustion/activation) of specific immune subpopulations including Tregs, cytotoxic T cells, and tumor-associated macrophages. Furthermore, peripheral blood will also be collected at baseline and after AI treatment to evaluate systemic changes of immune response after AI in responders vs. nonresponders.

[figure not shown]

Figure 1. The schematic representations of the study: The collection of pre-treated biopsies from breast cancer patients with estrogen receptor positive (ER+) and human epidermal growth receptor 2 negative (HER2-) is shown. The obtained surgical specimens from good responders and bad responders (progressors) will be analyzed and compared with pre-treated samples. All analyses will be carried out through single nucleus RNA-sequencing.

We had experience working with patient samples with triple-negative breast cancer (TNBC). The purpose of the study is to show the impact of different combinations of chemotherapeutics on tumor microenvironment remodeling in bad responders (chemotherapy-resistant). Trichrome staining (a staining method to detect total collagen) was performed on both biopsies (before treatment) and surgical specimens (after treatment), which were obtained from the same patients, to compare the collagen expression level. Our findings showed that chemotherapeutics cause fibrosis, represented by higher collagen expression in the surgical specimens in comparison to collagen expression in biopsies (Figure 2) (1,2).

[figure not shown]

Figure 2. Trichrome staining of samples obtained from disease progressor patients with TNBC: Representative images show that different combination chemotherapy causes an increase in collagen content in the tumor microenvironment (*p<0.01).

subpopulations in doxorubicin (dox) sensitive vs. resistant murine TNBC models. For this study, doxorubicin-resistant murine triple-negative 4T1 cells were developed and inoculated into a mouse mammary fat pad. Tumors were taken, fibroblasts were isolated and analyzed with 10x genomics single-cell RNA-sequencing. Our findings showed that the fibroblasts which were isolated from dox-resistant tumors activated overexpression of collagen-related genes (Figure 3).

There have been several studies addressing the issues on the impact of chemotherapeutics on different cell populations in breast tumors (3, 4). The amount of infiltrated immune cell populations into breast tumors, for example, has been strongly related to the response to chemotherapy (5). However, not much is known about the impact of AIs on the cell populations of breast tumors. A very appreciated effort from Miller and colleagues reported their findings on patients who developed letrozole resistance (6). This study, however, was unfortunately limited by bulk RNA-based gene expression profiling.

In our project, by the help of single nuclei RNA-sequencing, we will be able to analyze the expression profile of the different type of tumor cell populations before and after letrozole treatment. This will provide an intensive analysis identifying novel markers predicting for response and understanding molecular mechanisms of resistance.

[figure not shown]

Figure 3. Development of doxorubicin resistant 4T1 cells and the gene expression profile of fibroblasts isolated from resistant 4T1 tumor: The development of doxorubicin resistant 4T1 cells from sensitive cells through stepwise dose increase and schematic explanation of resistant cancer cells are shown (a). Representative microscopy images demonstrate p-glycoprotein (red) expression and intracellular uptake of doxorubicin (red) in sensitive and resistant 4T1 cells (b). The schematic representation shows inoculation of sensitive and resistant 4T1 cells into mammary fat pad (c). Similar growth rate of sensitive and resistant tumors is shown (d). The analysis of different cell populations in sensitive and resistant tumors is shown (e). Four clusters, 0; epithelial cells, 1; fibroblasts and 3; macrophages and 3; endothelial cells are shown (f). Selected top 10 genes in cell clusters are shown (f). The heat-map analysis of top 10 genes for each cluster is shown (h). These results show that the fibroblasts overexpress extracellular matrix related protein, such as collagens, which can cause fibrosis (i).

1.2 Investigational Agent

Letrozole is an aromatase inhibitor, which is a commonly used endocrine therapy for breast cancer as per standard of care. Letrozole is an oral agent commonly supplied as a tablet.

2 Study Objectives

Our approach is to study the impact of AIs on not only cancerous cells but also on noncancerous cells in the tumor microenvironment. We seek to characterize factors discriminating non-responders from responders to AI early during treatment by analyzing different cells. We also aim to work on the impact of AIs on the immune landscape, as a noncancerous cell subpopulation, of AI-sensitive and AI-resistant tumors. This, we believe, will contribute to the current knowledge to improve the therapeutic efficacy of current treatment modalities, including chemotherapy and immunotherapy. Accordingly, we hypothesize that snRNA-seq can uncover hidden transcriptomic heterogeneity and underlying preexisting mechanisms driving AI resistance when analyzed at the single-cell level. Moreover, our research will also shed more light on the impact of estrogen deprivation on the immune landscape with AI treatment.

Primary Objective

1. To comprehensively evaluate differences in tumor microenvironment subpopulations in AI-sensitive vs. AI-resistant HR+ breast cancer.

Secondary Objective

1. To assess the effects of estrogen deprivation on the systemic immune response.
2. To assess the effects of estrogen deprivation on tumor immune microenvironment.

3 Study Design

This is a pilot study to evaluate the effects of aromatase inhibitor using single cell sequencing technology to evaluate both cancerous cells and tumor microenvironment.

[figure not shown]
3.1 General Description

This is a prospective study to collect tissue samples from patients with early-stage hormone receptor-positive HER2-negative breast cancer. Patients with newly diagnosed hormone receptor-positive HER2-negative invasive breast cancer will be approached by the study team prior to surgery. If there is no indication for neoadjuvant therapy and the patient can proceed with surgery, the patient will be registered and start on aromatase inhibitor with letrozole 2.5 mg oral daily for 2-8 weeks until surgery as part of their standard of care. Both archival biopsy and surgical specimens will also be collected for single-cell sequencing. For patients who screen fail and do not consent to future research, tissue and blood will be discarded.

Peripheral blood prior to and after letrozole treatment will also be collected.

Estrogen receptor, progesterone receptor, HER2, and Ki-67 will be evaluated in both biopsy and surgical specimens as per standard of care. Tumors with persistent elevation of Ki-67 $\geq 10\%$ after

2-8 weeks of letrozole will be classified as non-responders, and tumors with Ki-67 < 10% after treatment will be classified as responders.

3.2 Number of Subjects

Up to 50 patients

3.3 Duration of Participation

2-8 weeks

3.4 Primary Study Endpoints

To comprehensively evaluate differences in tumor microenvironment subpopulations in AI-sensitive vs. AI-resistant HR+ breast cancer.

3.5 Secondary Study Endpoints

1. To assess the effects of estrogen deprivation on the systemic immune response.
2. To assess the effects of estrogen deprivation on tumor immune microenvironment.

4 Subject Selection Enrollment and Withdrawal

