5.3 Drug Accountability

Drug accountability will be performed via patient pill diaries and patient appointments.

6 Study Procedures

This is a prospective study to collect tissue samples from patients with early-stage hormone receptor-positive HER2-negative breast cancer. Patients with newly diagnosed hormone receptor-positive HER2-negative invasive breast cancer will be approached by the study team prior to surgery. Once pathology confirms the diagnosis for hormone receptor-positive HER2 negative invasive breast cancer, the patient will be evaluated by breast surgeons. If there is no indication for neoadjuvant therapy and the patient can proceed with surgery within 2-8 weeks, the patient will be considered registered and start on aromatase inhibitor with letrozole 2.5 mg oral daily for 2-8 weeks until surgery as part of their standard of care. Patients will take letrozole until within 48 hours prior to surgery. Both archival biopsy and surgical specimens will also be collected for single-cell sequencing.

Peripheral blood will be drawn at two timepoints: 1.) prior to letrozole treatment and 2.) at least two weeks after the start of letrozole treatment, but prior to surgery.

Estrogen receptor, progesterone receptor, HER2, and Ki-67 will be evaluated in both biopsy and surgical specimen as per standard of care. Tumors with persistent elevation of Ki-67 \geq 10% after

2-8 weeks of letrozole will be classified as non-responders, and tumors with Ki-67 < 10% after treatment will be classified as responders.

This study is not utilizing the Cancer Center Registration Application. Patients will be considered enrolled upon completion of the ICF in PTrax. However, patients will not be considered registered within the Cancer Center until they have met all eligibility criteria and have a status of accrued in PTrax.

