6.1 Test Schedule

Tests and Procedures	Screening	Baseline (Day 1 of Letrozole)	After 2-8 weeks of Letrozole	Surgery ²
Visit Window	-30 days from baseline	-7 days		
Standard of Care Procedures				
Consent	X			
History and Physical		X	X ⁵	
Adverse event assessment		X	X ⁵	
Tissue collection	X ¹			X ¹
Research Procedures				
Blood samples		X ³	X ³	
- Sodium heparin (green top)				
10 mL x 6 tubes				
- Serum (red top) 10 mL x 1 tube				

¹ Archival sample collection from the standard of care biopsy and surgical resection at least 5 x 5 uM slides will be collected.

² Surgery should occur less than 48 hours after the last dose of letrozole.

³ Completed at two timepoints: 1.) prior to letrozole treatment and 2.) at least two weeks after the start of letrozole treatment, but prior to surgery.

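### Both secondary endpoints claim an effect of estrogen deprivation from a before/after comparison with no untreated group; for tumor tissue, treatment is also fully confounded with biopsy versus resection

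*Combined protocol and SAP*

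**What the plan says.** Section 3.5 words the two secondary endpoints as "To assess the effects of estrogen deprivation on the systemic immune response" and "To assess the effects of estrogen deprivation on tumor immune microenvironment". Section 2 has the same wording as secondary objectives, and the Endpoints text after Section 6.3 repeats it as Sub Aims 2A and 2B.

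On design, Section 3.1 says "This is a prospective study to collect tissue samples from patients with early-stage hormone receptor-positive HER2-negative breast cancer". Registered patients "start on aromatase inhibitor with letrozole 2.5 mg oral daily for 2-8 weeks until surgery as part of their standard of care". The Study Summary gives the reference therapy as not applicable.

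For tumor tissue, Section 6 (Study Procedures) says "Both archival biopsy and surgical specimens will also be collected for single-cell sequencing", and note 1 to the Section 6.1 schedule says "Archival sample collection from the standard of care biopsy and surgical resection at least 5 x 5 uM slides will be collected". For blood, Section 6 sets one draw before letrozole and a second "at least two weeks after the start of letrozole treatment, but prior to surgery". Section 1.1 adds that "peripheral blood will also be collected at baseline and after AI treatment to evaluate systemic changes of immune response after AI in responders vs. nonresponders".

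The statistical text in and after Section 6.3 says who analyzes the sequencing data and how long one step takes. It gives no model, adjustment or stated limitation for the before/after comparison.

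**The concern.** The endpoints name a cause, while the design observes only a change. With everyone treated, nothing in the data shows what the change would have been over the same weeks without letrozole. For tissue there is a second source of difference: a diagnostic biopsy and a surgical resection are different kinds of specimen, and every patient moves from one to the other just as she moves from untreated to treated.

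At stake is the conclusion drawn from the secondary aims. A systematic difference between biopsy and resection tissue could be reported as an immune effect of letrozole. The risk is not remote. In Section 1.1 the sponsor compares biopsies with surgical specimens from treated triple-negative patients and concludes that chemotherapy produces fibrosis, with no untreated biopsy-to-surgery comparison described.

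**Working it through.** **No plan figure to reproduce.** Section 6.3 declines a power calculation. The sample size (Section 3.2, up to 50) is not derived, and no alpha, test, effect size or SD is stated. The main check is therefore a reading of what the design can identify.

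**Step 1: what the mean change estimates.** Let δ be the mean letrozole effect, s the mean shift from biopsy to resection tissue, and τ the mean shift from elapsed time, recovery from biopsy and other concurrent changes.

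- Blood (endpoint 1): same specimen type at both times, second draw before surgery. Mean change = δ + τ.
- Tumor (endpoint 2): archival biopsy, then surgical specimen. Mean change = δ + s + τ.

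All patients have the same treatment sequence and, for tissue, the same specimen sequence. The terms cannot be separated at any sample size.

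**Step 2: whether a contrast inside the study recovers δ.**

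- Responders (R) minus non-responders (N), difference in change for tissue: (δ_R − δ_N) + (s_R − s_N) + (τ_R − τ_N). Only shifts common to both groups cancel, and what remains is a difference between two treated groups, not δ. The groups are defined by Ki-67 after treatment, at a 10% cut (Section 3.1).
- Change against days on letrozole, x (2–8 weeks is 14–56 days). Section 6 has letrozole continue until within 48 hours of surgery, so for tissue x is nearly the time elapsed from baseline to surgery. With linear terms, change = s + (δ′ + τ′)x, where δ′ and τ′ are the daily drug effect and daily drift. A constant specimen shift goes into the intercept, but the slope estimates only the sum δ′ + τ′. Duration is also not randomized.

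**Step 3: illustration of false attribution.** All inputs except n = 50 are assumed: true drug effect zero, two-sided paired t-test at 5%, pre/post correlation 0.5, non-drug shift b.

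- SD of the paired difference = SD × √(2(1 − 0.5)) = 1 SD.
- Non-centrality λ = b√n. For n = 50, √50 = 7.071, so λ = 1.414, 2.121 and 3.536 at b = 0.2, 0.3 and 0.5.
- Rejection probability = P(|T| > t_0.975,n−1), with T non-central t on n − 1 degrees of freedom and non-centrality λ.

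| Pairs | b = 0.1 | b = 0.2 | b = 0.3 | b = 0.5 |
|---|---|---|---|---|
| 50 | 0.107 | 0.284 | 0.548 | 0.934 |
| 40 | 0.095 | 0.235 | 0.457 | 0.869 |
| 25 | 0.077 | 0.161 | 0.302 | 0.670 |

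For any given non-drug shift, more pairs make a false attribution more likely. Recruiting more patients does not help.

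**The case against.** The strongest reply is that this is a pilot with no stated hypothesis test, alpha or efficacy conclusion. On that view the endpoint wording is ordinary language for an objective, and paired samples are a sound way to describe within-patient change. Section 1.1 already describes the blood aim as changes after treatment. Much of this stands: the samples and assays are suitable for describing change, and the documents do not say how a result will be reported. It does not remove the point, because the causal wording recurs in the objectives, endpoints and sub-aims, and the sponsor's own background draws a causal conclusion from the same kind of contrast.

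Three stronger readings are tempting, and the documents do not support them.

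- A reader might infer that the biopsy-to-resection switch affects both secondary endpoints. It does not. The systemic endpoint uses peripheral blood at both times, with the second draw before surgery.
- A reader might infer that the responder contrast, or a regression on days on letrozole, can stand in for a control. Step 2 of the working shows that neither can. The responder contrast is also not new for blood, since Section 1.1 already describes it.
- A reader might take the 28%, 55% and 93% as expected error rates for this study. They show only that a shift of that size would be detected. The documents give no evidence of its size, or that one exists.

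**Conclusion.** The point holds for both secondary endpoints on the missing comparison, and for the tumor endpoint alone on specimen type. The design supports a description of change from before to after letrozole; it does not support attributing that change to estrogen deprivation. For tissue the confounding with specimen type is complete.

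This conclusion rests on the documents' description of treatment and sampling and needs no numerical assumption. The false-attribution rates do: they depend on the assumed shift, a correlation of 0.5, a 5% paired test and the number of evaluable pairs. The change is worth making because it is cheap and prevents an unsupported conclusion, but it does not call into question the value of the samples or the pilot itself.

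**What to change.** 1. In Section 2, Section 3.5 and Sub Aims 2A and 2B, restate the secondary aims as *change from before to after letrozole* in the systemic immune response and in the tumor immune microenvironment. Reword the parent Specific Aim 2 to match.
2. State in the statistical section that this change cannot be attributed to estrogen deprivation alone, because there is no untreated comparison. For both endpoints, name elapsed time, recovery from biopsy and other concurrent changes.
3. For the tumor endpoint only, add that the change is confounded with biopsy versus resection tissue.
4. The difference in change between responders and non-responders may be reported for tissue as well as blood, labeled exploratory. Say that it removes only a specimen or time shift common to both groups, that the groups are defined by post-treatment Ki-67, and that it is not an untreated control.
5. Do not base any letrozole-related inference on a regression of change on days on letrozole, because duration is not randomized and coincides with elapsed time.

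The cost is wording and a weaker claim for the secondary aims. No patients, visits, samples or assays are added.

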4.1 Inclusion Criteria

Screening inclusion criteria

1. Female \geq 18 years.
2. Postmenopausal and suitable to receive aromatase inhibitor as per physician's discretion.
3. Histologically confirmed un-resected operable invasive adenocarcinoma of the breast ≥ 0.5 cm with estrogen receptor (ER) and/or progesterone receptor (PR) positive $\geq 10\%$, and no human epidermal growth factor receptor 2 (HER2) amplification or overexpression.
4. Patients must not have received any prior chemotherapy, radiation therapy, or endocrine therapy for their current breast cancer. Patients who received tamoxifen or raloxifene or another agent for prevention of breast cancer may be included.
5. Willing and able to provide research tissue samples.
6. Willing and able to provide research blood samples.

4.2 Exclusion Criteria

1. Immunocompromised patients including patients known to be HIV positive or those on chronic steroids.

NOTE: Must be off systemic steroids at least 14 days prior to pre-registration. However, topical steroids, inhalants or steroid eye drops are permitted.

2. Known history of active autoimmune disease that has required systemic treatment within ≤ 30 days (i.e., with use of disease modifying agents, corticosteroids, or immunosuppressive drugs) prior to pre-registration.

NOTE: Replacement therapy (e.g., thyroxine, insulin, or physiologic corticosteroid replacement therapy for adrenal or pituitary insufficiency) is not considered a form of systemic treatment. Patients with vitiligo, Graves disease, or psoriasis not requiring systemic treatment within the past 30 days are not excluded. Patients with Celiac disease controlled with diet modification are not excluded.

4.3 Subject Recruitment, Enrollment and Screening

This is a prospective study to collect tissue samples from patients with early-stage hormone receptor-positive HER2-negative breast cancer. Patients with newly diagnosed hormone receptor-positive HER2-negative invasive breast cancer will be approached by the study team prior to surgery. Patients will be screened by a study team member through provider list or schedule list. Patients will be contacted preferably via a phone call prior to their visit or in person at the time of their visit. Patients will be consented either electronically remotely via email or in person at the time of their visit by a study team member.

